6.2.8. Telephone Follow-up (At least 28 days following last dose of study drugs)

This visit should occur at least 28 days following the last dose of study drugs. This visit can be combined with the End of Study visit as long as it occurs at least 28 days following the last dose of study drugs. If it is not combined with the End of Study visit, this visit can be performed over the phone. There is a +14 day window for the telephone follow-up.

- AE assessment.
- Pregnancy status.

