- l. QuantiFERON Gold[®]™ in-Tube Test will be performed for ALL subjects (those who meet LDA and those who do not meet LDA at week 24) in Belgium, Czech Republic, Germany, Hungary, Italy, Poland, Spain, and the United Kingdom. For all other countries the test will ONLY be performed for subjects who do not achieve LDA at Week 24 and are therefore not randomized.
- m. Report and assess AEs within appropriate reporting period. See Section 6.1 for details.
- n. Height will not be collected in the Case Report Form (CRF).
- o. Can be combined with the End of Study visit as long as the Telephone Follow-up occurs at least 28 days after last administration of study drugs.
- p. Includes a query of pregnancy status in addition to AEs.
- q. Assessment of new physical findings consists of an abbreviated physical examination assessing the following: weight, vital signs, skin examination including a careful examination for melanoma and nonmelanoma skin cancer, lungs, heart, lower extremities for peripheral edema, abdomen, and lymph nodes.

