2.2. Endpoints

2.2.1. Efficacy Endpoints

2.2.1.1. Primary Efficacy Endpoint

Change in DAS28-4 (ESR) score from randomization (at Week 24) to the end of double-blind MTX withdrawal phase (at Week 48).

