6.2.7. Visit 6 (End of Study Visit; Week 48; Day 336/Early Withdrawal Visit)

Subjects who did not achieve LDA at Week 24 and were therefore not randomized do not require a separate EOS visit except for QuantiFERON Gold[®]™ In-Tube Test.

There is a ±10 day window for this visit. Subjects are required to fast for 6 hours prior to the visit. Procedures to be performed at Visit 6 include:

- Complete Physical Examination: height, weight, vital signs, general appearance, skin (presence of rash or suspicious lesions), HEENT (head, eyes, ears, nose and throat), lungs (auscultation), heart (auscultation for presence of murmurs, gallops, rubs), lower extremities (peripheral edema), abdominal (palpation and auscultation), neurologic (mental status, station, gait, reflexes, motor and sensory function, coordination) and lymph nodes.
- Laboratory testing including blood chemistry, hematology, CRP, lipid profile (fasting), ESR.
- 12-lead electrocardiogram.
- Biospecimen collection for banking.
- Pregnancy testing must be completed for all women of childbearing potential: all subjects must test negative; confirmation and documentation of the use of 2 highly effective methods of contraception by subjects of childbearing potential or their

partners must be done. For contraception and reproductive status details to be applied in Belgium, Czech Republic, Germany, Hungary, Italy, Poland, Spain, and the United Kingdom see [Appendix 7](#).

- 28 tender /painful and swollen joint counts.
- Completion of the following assessments:
 - Subject assessment of arthritis pain.
 - Subject global assessment of arthritis.
 - Physician global assessment of arthritis.
 - HAQ DI.
 - SF 36 (Version 2, Acute).
 - EuroQol EQ 5D.
 - WPAI Questionnaire.
 - FACIT Fatigue Scale.
 - US and Canada ONLY: RAPID3.
- Safety Assessment and AE reporting.
- Assess safety events for adjudication by the appropriate adjudication or review committee and collect biopsies of potential malignancy events for central laboratory pathologist over read and report to Pfizer Study Team or designee.
- Concomitant Medication Review.
- Review of dosing diary with the subject (the diary will be returned at this visit).
- Return unused investigational products.

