Appendix 1.2. Definition and Use of Visit Windows in Reporting

Visit windows will be used for efficacy variables, and for any safety displays that display by week.

If more than one observation from the same subject falls into the same visit window, the value closest to the targeted day will be used as the observation for that week. If two visits are equal distant from the Targeted Day in absolute value, the later visit should be used. All observations will, however, be included in the listings.

For endpoints derived from multiple components, eg, DAS28-4(ESR), each component will be windowed to select the value for analysis at a specific visit, and the value of the endpoint will then be derived. This means the component values may be from different visit dates that fall within the analysis window.

Subjects’ observations will be excluded from visit windows if the data was collected more than 7 days off study drug. (Safety analysis may follow Pfizer standard.)

Visit Label	Targeted Day	Analysis window for data sets
Open-Label Run-In Phase		
Baseline	Day 1	Last Observation up to and including First Dosing Date (no earlier than Day -90)
Week 6	Day 42	Days 2 – 63
Week 12	Day 84	If there is Week 6 visit such as lab tests: Days 64 – 126; If no Week 6 visit: Days 2 – 126
Week 24	Day 168	Day 127 – Discontinuation Day /Randomization Day (the earlier one)
Double-Blind Phase		
Randomization (Week 24)	Randomization Day	Last Observation up to and including First Dosing Date in Double-Blind Phase (no earlier than Day 127)
Week 36	Randomization Day + 84	Randomization Day + 1 – Randomization Day + 126
Week 48	Randomization Day + 168	Randomization Day + 127 –

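### Merging the 28-day follow-up with the Early Withdrawal visit can push a subject's exit efficacy scores past the SAP's 7-day off-drug limit

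*Protocol*

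**What the plan says.** - **Permission to merge.** Protocol 6.2.8 places the telephone follow-up at least 28 days after the last dose, with a window of +14 days, and adds: "This visit can be combined with the End of Study visit as long as it occurs at least 28 days following" the last dose. Footnote o of the Schedule of Activities says the same: "Can be combined with the End of Study visit as long as the Telephone Follow-up occurs at least 28 days" after the last administration. Neither text confines the option to safety items or to particular subjects.
- **What Visit 6 carries.** Under Protocol 6.2.7, one visit serves as the Week 48 (Day 336) End of Study visit and as the Early Withdrawal visit. It collects the joint counts, ESR and subject global assessment that make up DAS28-4(ESR), and the other efficacy measures. Its window is ±10 days.
- **Timing after withdrawal.** Protocol 6.3 tells the site to ask a withdrawing subject to come back for a final visit, but sets no deadline. The same section discontinues anyone off investigational product for more than 14 consecutive days.
- **What the SAP keeps.** Appendix 1.2 states that subjects' "observations will be excluded from visit windows if the data was collected more than 7 days off study drug", and makes an allowance only for safety analyses. The missing score then falls under SAP 6.1.1.1, where the MMRM assumes values are missing at random.

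**The concern.** The protocol sets a minimum delay for a combined visit, and the SAP sets a maximum delay for a usable efficacy score. The minimum (28 days) exceeds the maximum (7 days). A site that uses the permission for an early withdrawal breaks no protocol rule on visit timing and still produces an exit assessment that the efficacy analysis must discard.

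The value lost is a post-randomization DAS28-4(ESR). After randomization the schedule has only two efficacy visits, Week 36 and Week 48, so a subject who leaves before Week 36 may have no other score. Protocol 6.3 makes an uncontrolled flare a reason for discontinuation, so some exit scores may carry information about response that earlier scores do not. The SAP's multiple imputation (SAP 5.3) draws from the observed mean and SD by arm and time point, so it would not reveal a departure from missing at random.

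**Working it through.** **Inputs.** Merge allowed from 28 days after the last dose, contact window +14 days (Protocol 6.2.8). Visit 6 at Day 336 ±10 days (Protocol 6.2.7). Discontinuation after more than 14 consecutive days off product (Protocol 6.3). Efficacy exclusion after more than 7 days off drug; Week 36 window from Randomization Day +1 to +126 with target +84; Week 48 window from +127 (SAP Appendix 1.2; its upper end is cut off in the text available).

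**1. Any combined visit against the 7-day rule.** A combined visit falls 28 to 28 + 14 = 42 days after the last dose. The shortfall is at least 28 − 7 = 21 days, so its efficacy values are always excluded.

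**2. Completers.**
- Visit 6 window: 336 − 10 = Day 326 to 336 + 10 = Day 346.
- Last dose on Day 336: earliest combined visit 336 + 28 = Day 364, which is 364 − 346 = 18 days past the window.
- Last dose on Day 326: earliest combined visit 326 + 28 = Day 354, still 8 days past the window.
- For a combined visit on or before Day 346, the last dose must be on or before 346 − 28 = Day 318. The subject is then at least 28 days off product, beyond the 14-day rule.

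No combined visit satisfies the window, the 14-day rule and the 7-day rule together.

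**3. Early withdrawals.** The ±10 days is attached to Day 336 and does not bound an early exit visit. Illustrative last-dose days, counted from randomization:

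| Last dose | Prompt exit, by +7 | Combined exit, from +28 | Effect of merging |
|---|---|---|---|
| +60 (before Visit 5) | +67, Week 36 window | +88, excluded | No scheduled post-randomization DAS28 remains |
| +100 (Visit 5 done near +84) | +107, Week 36 window | +128, excluded | None: Visit 5 is closer to +84 and is the value analysed |
| +130 (Visit 5 done) | +137, Week 48 window | +158, excluded | Week 48 value lost, Week 36 value kept |

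Merging therefore costs an analysed value when the exit comes before Visit 5 (or Visit 5 was missed), or when a prompt exit would have fallen after +126. It costs nothing for a subject who would have been seen more than 7 days off drug anyway.

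**4. Scale.** The plan's sample size reproduces. With margin 0.6, SD 1.4, true difference 0 (assumed; not stated), one-sided 0.025 and 90% power:

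n per arm = 2 × (1.960 + 1.282)² × 1.4² / 0.6² ≈ 114.4, so 115 per arm and 230 in total, against 232 planned.

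At 116 per arm, power = Φ(0.6 / (1.4 × √(2/116)) − 1.960) = 90.4%. The documents give no rate of merging. Purely as an assumption, if 2%, 5% or 10% of Week 48 values were lost for any reason and the MMRM recovered nothing from Week 36, power would be 89.8%, 88.9% or 87.2%. The share lost to merging alone is unknown and can arise only among early withdrawals.

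**The case against.** The strongest reply is that the permission is optional and conditional. It does not move Visit 6 or ask anyone to stop drug. Protocol 6.2.1 wants visits as near as possible to the scheduled day, and 5.4.2 supplies drug to cover the window. Read with these, the clause mainly suits subjects who are already long off drug when they are seen, and their scores are lost to the SAP rule whether or not the visits are merged. This largely stands and sets the limits of the point. It does not cover the early withdrawal who could have been seen promptly, because nothing in the protocol sets a deadline for that visit.

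A reader might infer three stronger things, none of which the documents support:

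- **That completers lose their Week 48 endpoint by following the schedule.** Step 2 shows that a completer can merge only by breaching another rule.
- **That off-drug scores blur the arms toward non-inferiority.** This would require the scores to be analysed. SAP Appendix 1.2 removes them, and nothing in the plan proposes to relax that.
- **That a definite number of scores is lost.** No merge rate is given, and applying an assumed rate to all 232 randomized subjects would count completers who cannot properly merge.

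Nor do the documents show that most early withdrawals are flares. Protocol 7.23 lists many laboratory, infection and other safety reasons, with no proportions.

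The main binary analyses are essentially untouched. Under SAP 5.3.3 to 5.3.5, non-responder imputation counts dropouts as non-responders even if they respond at the withdrawal visit. Only the observed-case versions could lose a value.

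**Conclusion.** The point holds in a narrow form. The merge permission, the Visit 6 window, the 14-day rule and the SAP's 7-day rule are mutually inconsistent and must be reconciled. Every combined visit yields no usable DAS28-4(ESR) or other continuous efficacy value.

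The practical harm is limited to randomized early withdrawals who could have been assessed within 7 days of the last dose but whose visit is delayed in order to merge. Their exit score, in the Week 36 or Week 48 window depending on timing, becomes missing and is handled as missing at random. The number is not given and is probably small. The primary estimate is not contaminated, and the sample size is not in error. The case for acting is that the loss is avoidable, may be informative, and costs almost nothing to prevent. The conclusion assumes that the 7-day exclusion is applied as written and that at least some sites would use the option for subjects who could have been seen sooner.

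**What to change.** In Protocol 6.2.8 and footnote o, limit combining to subjects who are already at least 28 days off study drug when they are first available for Visit 6. In 6.2.7 or 6.3, state that Early Withdrawal efficacy assessments are to be done as soon as possible and, where feasible, within 7 days of the last dose, to match SAP Appendix 1.2. Keep the 28-day contact as a separate phone call. In the same edit, reconcile the merge wording with the ±10-day window and the 14-day rule. The change concerns the timing of assessments only.

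The cost is a few sentences in an amendment or administrative letter, and for each affected subject one phone call that the schedule already contains. No clinic visit is added, and no analysis changes.

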6.3. Subject Withdrawal

Subjects may withdraw from the study at any time at their own request, or they may be withdrawn at any time at the discretion of the investigator or sponsor for safety or behavioral reasons, or the inability of the subject to comply with the protocol-required schedule of study visits or procedures at a given study site. A complete list of specific discontinuation criteria for this study is listed in [Section 7.23](#).

If a subject does not return for a scheduled visit, every effort should be made to contact the subject. All attempts to contact the subject and information received during contact attempts must be documented in the subject's medical record. In any circumstance, every effort should be made to document subject outcome, if possible. The investigator should inquire about the reason for withdrawal, request that the subject return all unused investigational product(s), request that the subject return for a final visit, if applicable, and follow up with the subject regarding any unresolved adverse events (AEs).

If a subject completely withdraws from the study, and also withdraws consent for disclosure of future information, no further evaluations should be performed, and no additional data should be collected. The sponsor may retain and continue to use any data collected before such withdrawal of consent.

If a subject has discontinued investigational product for greater than 14 consecutive days, the subject will be discontinued from the study.

Subjects who experience a single episode of disease flare at any time during the study (including the open-label run-in and double-blind phase) that could not be controlled by rescue medications will be discontinued from the study.

7. ASSESSMENTS

Every effort should be made to ensure that the protocol-required tests and procedures are completed as described. However, it is anticipated that from time to time there may be circumstances, outside of the control of the investigator that may make it unfeasible to perform the test. In these cases the investigator is to take all steps necessary to ensure the safety and well-being of the subject. When a protocol-required test cannot be performed, the investigator is to document the reason for this and any corrective and preventive actions that he or she has taken to ensure that normal processes are adhered to as soon as possible. The study team is to be informed of these incidents in a timely fashion.

7.1. Physical Examination

A complete physical examination will be performed at the Screening Visit, Baseline Visit (Visit 1) and End of Study Visit (Visit 6). The following parameters and body systems will be examined and any abnormalities described: height (not required for Baseline Visit/Visit1), weight, vital signs, general appearance, skin (presence of rash, skin lesions with malignant features), HEENT (head, eyes, ears, nose and throat), lungs (auscultation), heart (auscultation for presence of murmurs, gallops, rubs), lower extremities (peripheral edema), abdominal (palpation and auscultation), neurologic (mental status, station, gait, reflexes, motor and sensory function, coordination) and lymph nodes.

7.2. Assessment of New Physical Findings

At all other visits (Visits 2-5), an abbreviated physical examination will be performed assessing the following: weight, vital signs, skin examination including careful examination for melanoma and non-melanoma skin cancer, lungs, heart, lower extremities for peripheral edema, abdomen and lymph nodes. Any clinically significant changes from the last complete physical examination should be recorded as AEs; ongoing AEs should be updated, as appropriate.

7.3. Chest Radiograph

A chest radiograph or chest CT scan will be obtained at the Screening Visit in all subjects, unless it has been taken and documented within the 3 months prior to the Screening visit. To be considered eligible for the study, the chest radiograph must be negative for active tuberculosis infection.

Screening for latent and/or active TB will be conducted using the QuantiFERON[®]-TB Gold In-Tube test. All subjects with positive results must have a chest radiograph performed and the radiograph must be negative for active tuberculosis infection. Subjects identified as having latent TB should be treated appropriately (see [Section 5.8.1.1](#)).

Chest computed tomography (CT) scans will not be performed as part of the study procedures. However, if a chest CT scan has been performed for other reasons within the 3 months prior to a scheduled chest radiograph, subjects do not need a new chest radiograph, but rather, the results of the chest CT scan may be used to confirm the absence of active tuberculosis infection.

7.4. Electrocardiogram

A 12-lead electrocardiogram (ECG) will be obtained on all subjects at the Screening Visit and at the End of Study visit. All ECGs should be performed after the subject has rested quietly for at least 10 minutes. ECGs will be read locally. All ECG results will be documented in the CRF and copies of the tracings maintained in the subject's source documentation. Subjects with a screening 12-lead electrocardiogram that demonstrates clinically significant abnormalities requiring urgent treatment (eg, acute myocardial infarction, serious tachy- or bradyarrhythmias) or that is indicative of serious underlying heart disease (eg, cardiomyopathy, major congenital heart disease, low voltage in all leads) should not be enrolled in the study.

End of Study ECGs will be compared to the Screening ECG and any clinically significant changes will be recorded as adverse events, and evaluated further, as clinically warranted.

7.5. Assessments of Disease Activity

Individual components for the following indicators of disease activity will be collected throughout the study as described in [Table 3](#) below.

Table 3. Disease Activity Indicators

Indicator	Definition/Calculation
DAS28-4 (CRP)	$0.56*\sqrt{(TJC28)} + 0.28*\sqrt{(SJC28)} + 0.36*\ln(\text{CRP in mg/l} + 1) + 0.014*\text{PtGA in mm} + 0.96$
DAS28-4 (ESR)	$0.56*\sqrt{(TJC28)} + 0.28*\sqrt{(SJC28)} + 0.70*\ln(\text{ESR in mm/ hour}) + 0.014*\text{PtGA in mm}$
Simplified Disease Activity Index (SDAI)	$(28TJC) + (28SJC) + [\text{PhyGA in cm}] + [\text{PtGA in cm}] + [\text{CRP in mg/dL}]$
Clinical Disease Activity Index (CDAI)	$(28TJC) + (28SJC) + [\text{PhyGA in cm}] + [\text{PtGA in cm}]$
American College of Rheumatology (ACR) Response Rates	The ACR's definition for calculating a 20% improvement in RA (ACR20) is as follows: a 20% improvement in tender and swollen joint counts and 20% improvement in 3 of the 5 remaining ACR-core set measures: subject and physician global assessments, pain, disability, and an acute-phase reactant (eg, CRP). Similarly, ACR50 and 70 are calculated with the respective percent improvements.
ACR/EULAR Boolean-based definition of remission	At any time point, a subject must satisfy all of the following: tender joint count ≤ 1 , swollen joint count ≤ 1 , CRP ≤ 1 mg/dL, subject's global assessment of health ≤ 1 on a 0-10 scale

TJC = tender joint count; SJC = swollen joint count; CRP = C-reactive protein in mg/L; ESR = erythrocyte sedimentation rate in mm/first hour, PtGA = subject's global assessment of health; PhyGA = physician's global assessment of health

7.6. Joint Counts

7.6.1. Tender/Painful Joint Count (28 Joint Count)

Twenty-eight (28) joints will be assessed by a blinded joint assessor to determine the number of joints that are considered tender or painful. The response to pressure/motion on each joint will be assessed using the following scale: Present/Absent/Not Done/Not Applicable (to be used for artificial joints).

The 28 joints to be assessed are the shoulders, elbows, wrists, metacarpophalangeal (MCP) joints, proximal interphalangeal (PIP) joints, and knees. Artificial joints will not be assessed.

7.6.2. Swollen Joint Count (28 Joint Count)

The blinded joint assessor will also assess these joints for swelling using the following scale: Present/Absent/Not Done/Not Applicable (to be used for artificial joints).

The 28 swollen joint count includes the following joints: shoulders, elbows, wrists, metacarpophalangeal joints (MCP), proximal interphalangeal joints (PIP), and knees. Artificial joints will not be assessed.

7.7. Subject Assessment of Arthritis Pain

Subjects will assess the severity of their arthritis pain using a 100 mm visual analog scale (VAS) by placing a mark on the scale between 0 (no pain) and 100 (most severe pain), which corresponds to the magnitude of their pain.

7.8. Subject Global Assessment of Arthritis

Subjects will answer the following question, “Considering all the ways your arthritis affects you, how are you feeling today?” The subject’s response will be recorded using a 100 mm VAS.

7.9. Physician Global Assessment of Arthritis

The Investigator will assess how the subject’s overall arthritis appears at the time of the visit. This is an evaluation based on the subject’s disease signs, functional capacity and physical examination, and should be independent of the Subject’s Global Assessment of Arthritis. The Investigator’s response will be recorded using a 100 mm VAS.

7.10. Health Assessment Questionnaire – Disability Index (HAQ-DI)

The HAQ-DI¹² assesses the degree of difficulty a subject has experienced during the past week in 8 domains of daily living activities: dressing and grooming, arising, eating, walking, hygiene, reach, grip, and other activities. Each activity category consists of 2-3 items. For each question in the questionnaire, the level of difficulty is scored from 0 to 3 with 0 representing “no difficulty,” 1 as “some difficulty,” 2 as “much difficulty,” and 3 as “unable to do”. Any activity that requires assistance from another individual or requires the use of an assistive device adjusts to a minimum score of 2 to represent a more limited functional status. The form should then be checked by the site staff for completeness.

